# 9.3 Handling of Partial Dates

If partial dates are recorded for adverse event and concomitant medications, then partially dates will be filled as per Appendix 3. No imputation will be done for other partial dates.

Confidential Page 31 of 57

## 9.4 Interim Analysis

This is an early closure study; no interim analysis will be performed.

# 9.5 Pooling Strategy for Study Sites

No pooling strategy will be performed due to the smaller number of subjects enrolled in the study.

#### 9.6 Visit Windows / Unscheduled Visits

Visit windowing will be applied for the analyses which use visit categories. For categorical visit summaries, all visits including early termination assessments and unscheduled visits will be included with the closest scheduled post-baseline visit that includes the efficacy or safety assessment, based on number of days since Day 1. For the primary variable of ERP P300 latency effect, if multiple assessments fall within the same analysis window, pre- and post-dose measurement will be averaged within the analysis window for this variable. For all other efficacy assessments, if multiple efficacy assessments fall within the same analysis window (other than baseline), any non-missing efficacy assessments will be averaged. For all non-efficacy assessments, a last-within-window approach will be used.

The analysis windows for ERP P300, ADAS-Cog13 and COWAT are:

	Protocol-Specified	Analysis-Specified
Analysis Visit	Day	Interval
Week 2	Day 14	Day 2-63
Week 12	Day 84	Day 64-112
Week 20	Day 140	Day 113-161
Week 26	Day 182	Day 162-196
Week 30	Day 210	Day 197-218

The analysis windows for C-SSRS, Physical and Neurological Exams, EG, Vital Signs, Labs are:

	Protocol-Specified	
Analysis Visit	Day	Analysis-Specified Interval
Week 2	Day 14	Day 2-28
Week 6	Day 42	Day 29-63
Week 12	Day 84	Day 64-98
Week 16	Day 112	Day 99-126
Week 20	Day 140	Day 127-161
Week 26	Day 182	Day 162-196
Week 30	Day 210	Day 197-218

The analysis windows for GDS are:

Confidential Page 32 of 57

	Protocol-Specified	
Analysis Visit	Day	Analysis-Specified Interval
Week 12	Day 84	Day 2-133
Week 26	Day 182	Day 134-196
Week 30	Day 210	Day 197-218

The analysis visit windows for MMSE is:

Analysis Visit	Protocol-Specified Day	Analysis-Specified Interval
Week 12	Day 84	Day 2-112
Week 20	Day 140	Day 113-161
Week 26	Day 182	Day 162-218

The analysis windows for MDS-UPDRS, NMSS, ADCS-ADL23, ADCS-CGIC, ADCS-CaGIC, ADCS-CGIS, and PK are:

Analysis Visit	Protocol-Specified Day	Analysis-Specified Interval
Week 12	Day 84	Day 2-133
Week 26	Day 182	Day 134-218

Confidential Page 33 of 57

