## 6.4 Safety Variables

#### 6.4.1 Adverse Events

AE reporting will begin at Screening (Visit 1) and will continue until the end of the study (28 days from last dose of IMP, Visit 9 – Safety Follow-up). AEs will be reported by the subject (or, when appropriate, by a caregiver, support person, or the subject's legally authorized representative).

The investigator and any designees are responsible for detecting, documenting, and recording events that meet the definition of an AE or SAE and remain responsible for following up AE (see Section 6.4.1.5).

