#### 7.4.2 Withdrawal from the Study

- A subject may withdraw from the study at any time at his/her own request, or may be withdrawn at any time at the discretion of the investigator for safety, behavioral, compliance, or administrative reasons, including protocol deviations
- Subjects must be discontinued from the study and/or receive no further study treatment, if any of the following criteria are met:
  - o Any of the stopping criteria described in Section 5.8
  - Any AE or safety finding that may jeopardize the subject's health in the investigator's judgment, and which is considered to be at least possibly related to the study drug.
  - Withdrawal of informed consent by subject/legally authorized representative. In the event that a subject's decision to withdraw from the study is motivated by adverse

event(s) or stated lack of efficacy, these reasons should be recorded as the reason for early termination.

- Physician decision
- Non-compliance with study drug
- Site terminated by sponsor
- Repeat incapacity of subject and/or caregiver (in the judgment of the investigator) to properly administer study drug despite training and testing
- o Prolonged or definitive loss of caregiver without adequate replacement
- Nursing home placement
- If the subject withdraws consent for disclosure of future information, the Sponsor may retain and continue to use any data collected before such a withdrawal of consent.
- If a subject withdraws from the study, he/she may request destruction of any samples taken and not tested, and the investigator must document this in the site study records.
- All subjects who prematurely discontinue from the study, i.e., prior to Visit 8 (Week 26), unless the cause is screen failure, should return for an early termination visit and complete all the assessments scheduled for the Week 26 visit (Visit 8); see the schedule of activities (Table 1) for data to be collected.
- Unless the reasons of premature discontinuation prevent further meaningful testing, investigators should make every effort to motivate subjects who discontinue early (and caregiver) to return for a Visit 8 (Week 26) for final assessments

Upon discontinuation of study drug, subjects will continue with their original treatment; tapering off study medication is not required.

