# 5.2 Secondary Objectives

- To evaluate the clinical efficacy of ATH-1017 separately on:
  - 1) Cognition and
  - 2) ERP P300 latency

Confidential Page 10 of 57

[figure not shown]
Table 1. Study Objectives and Associated Endpoints

Primary Objectives	Primary Endpoints	
To evaluate the clinical effects of ATH-1017 in subjects with PDD or DLB	The Global Statistical Test (GST) score (O'Brien, 1984) that combines the standardized change from baseline scores at Week 26 for cognition (Alzheimer's Disease Assessment Scale-Cognitive Subscale 13-item version [ADAS-Cog 13 ]) and ERP P300 latency, comparing ATH-1017 to placebo	
To determine the safety and tolerability of ATH-1017 in subjects with PDD or DLB	Analysis of adverse events (AEs), including injection site AEs; changes from baseline for the following variables: vital signs, 12-lead electrocardiogram (ECG), and laboratory tests (chemistry, hematology, urinalysis); concomitant medication assessments, physical and neurological exams, Columbia-Suicide Severity Rating Scale (C-SSRS), and Geriatric Depression Scale (GDS)	
Secondary Objectives	Secondary Endpoints	
To evaluate the clinical effects of ATH-1017 separately on: (1) cognition and (2) ERP P300 latency	
 
ADAS-Cog13 score: change from baseline at Weeks 2, 12, 20, and 26 compared to placebo
 
ERP P300 latency: change from baseline at Weeks 2, 12, and 26 compared to placebo
 
	

Confidential Page 11 of 57

Exploratory Objectives	Exploratory Endpoints

Confidential Page 12 of 57

Confidential Page 13 of 57

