#### 6.4.1.3 Follow-up of Adverse Events

All AEs experienced by a subject, irrespective of the suspected causality or seriousness, will be monitored until the event has resolved, until any abnormal laboratory values have returned to baseline or stabilized at a level acceptable to the investigator and Medical Monitor, until there is a satisfactory explanation for the changes observed or until the subject is lost to follow-up.

All AEs/SAEs that are still present after the last study drug administration (including AEs that have led to premature discontinuation), will be followed-up at the Safety follow-up visit. In case the AE/SAE is still ongoing after that timepoint, this will be followed up until its resolution or until otherwise agreed between the Sponsor and the investigator.

Additional safety data collected after the Safety follow-up visit to follow-up the ongoing AE will not be included into the clinical database, if this was already locked; therefore, the clinical database lock will not be delayed due to this situation. Any SAE will be followed up, if needed, after clinical database lock, and the information will be only stored in the safety database.

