# Appendix 1. Derivation of GST scores.

A composite approach will be utilized to derive the GST score for each patient at each visit in order to support an overall assessment of disease based on the combination of the clinical and functional scores (change from baseline ADAS-Cog13 and change from baseline ERP P300 latency).

The following notation will be used to compute the GST score. Let  $x_{ijk}$  and  $y_{ijk}$  will denote the changes from baseline to the kth visit for the jth patient in the ith trial arm (i=1 corresponds to placebo and i=2 corresponds to ATH-1017) for ADAS-Cog13 and ERP P300 latency, respectively. To simplify notation, it will be assumed that the number of patients in a trial arm does not depend on the visit, i.e.,  $n_1$  patients in the placebo arm and  $n_2$  patients in the ATH-1017 arm.

The GST score will be computed by applying the following algorithm to the ADAS-Cog13 and ERP P300 latency change scores. Beginning with ADAS-Cog13, the overall mean will be computed at the *k*th visit, i.e.,

 $m_k = \frac{n_1 \bar{x}_{1\cdot k} + n_2 \bar{x}_{2\cdot k}}{n_1 + n_2}$  where  $\bar{x}_{1\cdot k}$  and  $\bar{x}_{2\cdot k}$  are the arm-specific sample means. Next, the pooled standard deviation will be computed at the kth visit, i.e.,

$$s_k = \sqrt{\frac{(n_1 - 1)s_{1k}^2 + (n_2 - 1)s_{2k}^2}{n_1 + n_2 - 2}}$$

where  $s_{1k}^2$  and  $s_{2k}^2$  are the arm-specific sample variances. Finally, the standardized change scores will be defined as follows:

$$x_{ijk}^* = \frac{x_{ijk} - m_k}{s_k}$$

The standardized change scores for ERP P300 latency will be computed in a similar way and will be denoted by  $y_{ijk}^*$ .

The GST score for the change from baseline to the kth visit for the jth patient in the ith trial arm is defined as

$$(\frac{x_{ijk}^* + y_{ijk}^*}{2})$$

Note that a negative sign is applied to  $y_{ijk}^*$  since an increase in the ERP P300 latency score indicates an unfavorable response. This algorithm will be applied to each post-baseline visit. Note that the GST score calculation for each post-baseline visit is a composite of standardized change from baseline components. In order to provide a baseline value for GST for covariate purposes, the baseline GST score will also be calculated. The calculation at baseline is slightly different, using the observed baseline ADAS-Cog13 and ERP P300 latency values, instead of change from

Confidential Page 45 of 57

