- Subject hearing will be tested to establish suitability for ERP assessment (ability to hear or differentiate the 2 different tones necessary for auditory ERP P300 assessment, using the centrally provided ERP equipment); subjects who wear a hearing aid must remove their hearing aid during the Screening auditory test and during ERP P300 recordings.
- o ERP P300 will be performed at the Pre-baseline visit (Visit 2a, Day -10 to Day -3, no dosing); pre-dose and post-dose at Baseline/Day 1 (Visit 2b), Week 2 (Visit 3), Week 12 (Visit 5), and Week 26 (Visit 8). ERP P300 data should be uploaded for quality check immediately after the completion of the Pre-baseline visit (Visit 2a). ERP P300 will also be performed at Safety follow-up (Visit 9, no dosing).
  - Pre-dose ERP P300 assessments will be performed immediately preceding IMP dose but can be up to 1 hour before dose
    in clinic.
  - Post-dose ERP P300 assessments will be performed at approximately 2 (± 1) hours after dose.

Confidential Page 49 of 57

	Subjects who terminate prior to Visit 9 are to complete same assessments as Visit 8/ET (early termination). For clinica outcome assessments, if completed the assessment within 4 weeks of the ET visit they do not need to be repeated; all
	safety outcomes and drug accountability should be performed regardless of interval.
Safety	ADAS-Cog 13 , will be performed pre-dose. For visits after Baseline (except for follow-up when dosing is not applicable), all cognitive assessments will be performed post-dose, in the order of assessments, with ADAS-Cog 13 performed at approximately 1 hour (± 30 minutes) post dose.  C-SSRS and GDS may be completed any time at applicable visits.

Confidential Page 50 of 57

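### The window table shared by P300 and ADAS-Cog13 departs from the SAP's own closest-visit rule, and no rule keeps an early stopper's off-drug Visit 9 out of on-treatment visits

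*SAP*

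**What the plan says.** SAP 9.6 gives one rule for placing visits, including early termination and unscheduled ones: they "will be included with the closest scheduled post-baseline visit that includes the efficacy or safety assessment, based on number of days since Day 1". Several P300 records in one window are averaged. For safety data, "For all non-efficacy assessments, a last-within-window approach will be used".

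P300, ADAS-Cog13 and COWAT then share one table: Week 2 = Day 2-63, Week 12 = Day 64-112, Week 20 = Day 113-161, Week 26 = Day 162-196, Week 30 = Day 197-218.

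The two GST components have different schedules (SAP Table 1 and Appendix 2). The P300 endpoint is "ERP P300 latency: change from baseline at Weeks 2, 12, and 26 compared to placebo". It has no Week 20 assessment, but "ERP P300 will also be performed at Safety follow-up (Visit 9, no dosing"). ADAS-Cog13 is done at Weeks 2, 12, 20 and 26, and not at Visit 9.

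On the GST score, SAP Appendix 1 states: "This algorithm will be applied to each post-baseline visit".

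On timing after early stopping, Protocol 6.4.1 collects adverse events "until the end of the study (28 days from last dose of IMP, Visit 9"). SAP 6.4.1.3 says that adverse events still present after the last dose ("including AEs that have led to premature discontinuation), will be followed-up at the Safety follow-up visit"). Protocol 7.4.2 asks for an early termination visit and adds that "investigators should make every effort to motivate subjects who discontinue early (and caregiver) to return for a Visit 8 (Week 26) for final assessments". SAP 9.1 analyzes all collected data unless stated otherwise, and no on-treatment cut-off is stated.

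**The concern.** There are two problems.

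First, the shared table contradicts the sentence it is meant to implement. One set of windows cannot fit two measures with different visit schedules, and the Week 2/Week 12 boundary fits neither.

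Second, windows look only at study day. An off-drug Visit 9 from someone who stopped early can land in a window labelled Week 2, 12, 20 or 26. There its P300 may be averaged with on-drug values or stand as the only value. Laboratory, ECG and vital-sign results may displace on-drug values under the last-within-window rule, or fill a later on-treatment visit.

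The records exposed are termination, unscheduled and follow-up records, and they matter more in a trial that was stopped early. By-visit summaries are what SAP 10.5.6 keeps, and SAP 10.5.1 and 10.5.2 let the summary statistics decide whether the MMRM is run at all. A Week 20 GST would also be standardized on the mean and pooled SD of stray P300 records only.

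**Working it through.** **Method.** Assign each day from Day 2 to Day 218 (217 days) to the closest scheduled visit for that measure. The boundary is (earlier target + later target)/2, and a tie goes to the earlier visit, as in the SAP's own tables.

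**Reproducing the SAP's tables first**

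| Table | Target days | Computed upper bounds | SAP upper bounds |
|---|---|---|---|
| Safety | 14, 42, 84, 112, 140, 182, 210 | 28, 63, 98, 126, 161, 196, 218 | same |
| GDS | 84, 182, 210 | 133, 196, 218 | same |
| MMSE | 84, 140, 182 | 112, 161, 218 | same |
| MDS-UPDRS group | 84, 182 | 133, 218 | same |
| Shared P300/ADAS-Cog13, all five listed visits | 14, 84, 140, 182, 210 | **49**, 112, 161, 196, 218 | **63**, 112, 161, 196, 218 |

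Four tables reproduce exactly. The shared one fails even if both measures had all five visits: (14 + 84)/2 = 49, not 63. Day 63 is the Week 6/Week 12 midpoint, (42 + 84)/2, and neither measure is done at Week 6.

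**Each measure on its own schedule**

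- P300, targets 14, 84, 182, 210: boundaries 49, (84 + 182)/2 = 133, (182 + 210)/2 = 196. Mismatches:
  - Day 50-63, labelled Week 2, should be Week 12 (14 days).
  - Day 113-133, labelled Week 20, should be Week 12 (21 days).
  - Day 134-161, labelled Week 20, should be Week 26 (28 days).
  - Total 14 + 21 + 28 = 63; 63/217 = 29.0%.
- ADAS-Cog13, targets 14, 84, 140, 182: boundaries 49, (84 + 140)/2 = 112, (140 + 182)/2 = 161. Mismatches:
  - Day 50-63, labelled Week 2, should be Week 12 (14 days).
  - Day 197-218, labelled Week 30, should be Week 26 (22 days).
  - Total 14 + 22 = 36; 36/217 = 16.6%.

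Scheduled visits within ±7 days all fall in the right window.

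**Visit 9 of an early stopper.** Study day of Visit 9 = last-dose day + lag. Protocol 6.4.1 gives a lag of 28 days; the ±7-day tolerance gives a range of 21 to 35. Subtracting the lag from the current window bounds:

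| Lag | Last doses that put Visit 9 in Weeks 2-26 | Last doses that make it Week 26 P300 |
|---|---|---|
| 21 | up to 196 - 21 = Day 175 | Day 141-175 |
| 28 | up to 196 - 28 = Day 168 | Day 134-168 |
| 35 | up to 196 - 35 = Day 161 | Day 127-161 |

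**Example.** Last dose and termination visit are on Day 150; Visit 9 is on Day 150 + 28 = Day 178. The Day 150 P300 is labelled Week 20, which is not a P300 visit; by the stated rule it belongs to Week 26. The off-drug Day 178 P300 becomes the only Week 26 value.

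**Averaging.** With lag 28 and a termination P300 on the last-dose day, the two records share a window for last doses on Day 2-35, 64-84, 113-133 and 162-168.

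**The case against.** The strongest counter-case has five parts.

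1. **Visit 9 attendance is not established.** Footnote r of the Schedule of Assessments and Protocol 7.4.2 mention only termination or Visit 8 assessments, and the follow-up passages concern adverse events. This stands as a limit on the second problem. The gap remains, because nothing excludes such a record, and a late return for Visit 8 under Protocol 7.4.2 raises the same issue. Whether to use off-drug data is an estimand choice, but the SAP does not make it explicitly.
2. **The effect on the GST is narrower than on P300.** The GST needs both components, and ADAS-Cog13 is not done at Visit 9. In the Day 150 example no Week 26 GST forms. If the termination visit is on the last-dose day, Visit 9 enters a Week 26 GST only when both fall in Day 162-196. That means last doses on Day 162-168 at lag 28 (7 days), Day 162-175 at lag 21 (14 days), and none at lag 35. This stands; the ranges above are for P300.
3. **One table keeps the two components aligned.** This is a defensible aim, but the SAP does not state it and it does not explain Day 63.
4. **Some of the count is soft.** Of the 36 ADAS-Cog13 days, 22 lie in a window where none is scheduled. MMSE could be checked only against the days in its own table, because its schedule is not visible. Both are true, but the safety and GDS tables were checked against the Schedule of Assessments.
5. **The impact is small.** SAP section 8 allows no statistical conclusion, the MMRM is conditional, and listings keep the raw values. This stands and limits the weight of the point, but it does not remove the contradiction.

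**Conclusion.** Both parts hold. The shared table breaks the SAP's rule on 63 of 217 days for P300 and 36 for ADAS-Cog13; the other four tables show no mismatch. These are calendar days, not subjects. Windowing by study day alone would also count an early stopper's off-drug Visit 9 as on treatment for last doses up to Day 168 (Day 161 to 175 over lags of 35 to 21 days). That part assumes that early stoppers attend Visit 9.

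The number of affected subjects cannot be computed, because the documents give no termination dates or Visit 9 attendance. The damage is confined to by-visit summaries, GST scores and the MMRM if run. The point should be corrected, but it does not call the trial as a whole into question.

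**What to change.** **Separate windows that follow the stated rule**

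| Visit | P300 | ADAS-Cog13 |
|---|---|---|
| Week 2 | Day 2-49 | Day 2-49 |
| Week 12 | Day 50-133 | Day 50-112 |
| Week 20 | none | Day 113-161 |
| Week 26 | Day 134-196 | Day 162-218 |
| Week 30 | Day 197-218 | none |

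Set COWAT by the same rule from its own schedule, which is not visible in the public text.

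**GST.** Compute it only at Weeks 2, 12 and 26, with each component in its own windows, so that the scheduled Week 20 ADAS-Cog13 stays out of Week 26.

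**Off-drug records.** Map Visit 9 to the follow-up category by its nominal label, for efficacy and safety, whatever the study day. Flag other records after last dose (late termination visits, returns for Visit 8) as off-drug and state how by-visit summaries treat them, without a fixed one-day cut-off. Reconcile the passages on whether early stoppers attend Visit 9.

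Make these changes together. Re-windowing alone would widen the last doses that put Visit 9 into Week 26 P300 at lag 28 from Day 134-168 to Day 106-168 (134 - 28 = 106).

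**Cost.** One extra table and one flag; a few records change visit. A P300/ADAS-Cog13 pair from a termination visit on Day 113-161 gets different visit labels and yields no GST of its own. The same applies to a Day 150 P300 now paired with a Day 140 ADAS-Cog13 that footnote r lets the site not repeat. What is lost in each case is a GST at Week 20, where P300 is not scheduled.

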# 5.8 Stopping Criteria

For all subjects, at any time during the study, study treatment should be discontinued and the subject will be withdrawn immediately if any of the following criteria/AEs are recorded:

- ALT or AST  $> 5 \times ULN$  for more than 2 weeks
- ALT or AST  $> 8 \times$  upper limit of normal (ULN)
- ALT or AST > 3 × ULN and total bilirubin > 2 × ULN, or international normalized ratio [INR] > 1.5
- ALT or AST  $> 3 \times$  ULN with symptoms (the appearance of fatigue, nausea, vomiting, right upper quadrant pain or tenderness, fever, rash, and/or eosinophilia > 5%)
- AEs:
  - Any SAE confirmed as probably or definitely related to the IMP
  - Any AE of severe intensity confirmed as probably or definitely related to the IMP and associated with clinically significant findings
     (Note: causality as determined by the Sponsor)

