#### • ECG criterion:

QTcF > 500 msec (if prolonged QTcF interval is observed during the study, then a minimum of 2 repeat ECGs should be obtained over a brief period. The mean of the 3 ECGs will be used to determine this stopping criterion).

For QTcF readings that are borderline, or difficult to interpret due to e.g., presence of a branch bundle block, or in those where the T and U waves are superimposed or connected, a manual, local reading using the same ECG device should be considered to determine applicability of this ECG stopping criterion, in discussion with the Medical Monitor. Baseline conditions should be taken into account when considering the ECG stopping criterion (see Section 4.3, exclusion criterion #17).

In addition, if any of the above criteria are met, the event must be reported and discussed with the Medical Monitor.

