## 6.4.6 12-Lead Electrocardiogram

Standard safety 12-lead ECGs will be performed at Screening, at pre-dose and 30 ( $\pm$  15) minutes post-dose on Day 1 and 30 ( $\pm$  15) minutes post-dose at all other visits. All ECGs will be performed in triplicate, as detailed in the Schedule of Assessments (Table 1).

The 12-lead ECGs will be performed after the subject has been resting supine for  $\geq 5$  minutes. The ECG will include all 12 standard leads and a Lead II rhythm strip on the bottom of the tracing. The following ECG parameters will be collected: PR interval, QRS interval, RR interval, QT interval, and QTcF.

All ECGs must be evaluated by the investigator or qualified designee for the presence of abnormalities. Collection and analysis of ECG data will be performed by a central ECG vendor.

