## 10.6.3 Electrocardiograms

ECG values will be summarized by visit and treatment group using descriptive statistics (n, mean, median, SD, minimum, maximum) for PR interval, QT interval, QTcB interval, QTcF interval, RR interval, mean heart rate, and QRS duration.

The latest non-missing ECG value collected prior to dosing will be used as the baseline value. The baseline values will usually be the vital signs recorded at the Day 1 30 min pre-dose visit. In the case of repeated ECG parameters, the last collected values within that visit will be used for the summary tables.

ECG will be provided in a data listing by subject, treatment group, subject, visit, timepoint and parameter.

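### The SAP's by-visit ECG table keeps the last ECG in a window, on or off drug, with no worst on-treatment QTcF summary, so it need not show a QTcF above 500 msec that stopped a subject

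*SAP*

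**What the plan says.** SAP 9.6 allocates records by study day: "all visits including early termination assessments and unscheduled visits will be included with the closest scheduled post-baseline visit". Where several fall in one window, "For all non-efficacy assessments, a last-within-window approach will be used". Nothing limits the choice to ECGs taken on drug.

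SAP 10.6.3 adds a rule within a visit: "In the case of repeated ECG parameters, the last collected values within that visit will be used for the summary tables". The planned ECG output is descriptive statistics by visit and arm, plus a listing. There is no worst-value, maximum-change or threshold table for QTcF.

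Protocol 5.8 sets the stopping limit at QTcF above 500 msec. If a prolonged value is seen, "a minimum of 2 repeat ECGs should be obtained over a brief period", and "The mean of the 3 ECGs will be used to determine this stopping criterion". When a criterion is met, "study treatment should be discontinued and the subject will be withdrawn immediately if any of the following criteria/AEs are recorded". Protocol 6.4.6 requires every ECG in triplicate.

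Protocol 7.4.2 asks subjects who discontinue early to return for an ET visit with the Week 26 assessments, which include an ECG. Protocol 6.4.1 places Visit 9, which also has an ECG, 28 days from the last dose. Protocol 8.4 says ECG results will be summarized with frequency rates; Protocol 8.4.3 mentions only listing and descriptive summary. SAP section 6 keeps the safety listings and summaries despite the early stop.

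**The concern.** The value that stops a subject and the value that reaches the summary table are chosen by different rules. The first is a mean of 3 ECGs on drug. The second is whichever ECG comes last, including one taken after the drug was withdrawn because of that QTcF. The by-visit table is the only ECG summary in the SAP, and ECG change is part of the primary safety endpoint. Its maximum can look unremarkable in an arm that had a QTcF stop. Off-drug ECGs counted as treatment visits also mix two exposure states in one row, which would tend to dilute any on-drug effect.

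**Working it through.** The plan states no figure on this point, so there is none to reproduce. The check applies the SAP rules to the protocol schedule.

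**Inputs.** ECG windows: SAP 9.6. Visit days and the ±7-day allowance: Protocol Table 1. Visit 9 at last dose + 28 days: Protocol 6.4.1.

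| Visit | Target day | Window | Days left, on target | Days left, visit ±7 | Last dose + 28 | Tabulated as |
|---|---|---|---|---|---|---|
| Week 2 | 14 | 2-28 | 28 - 14 = 14 | 7-21 | 42 | Week 6 |
| Week 6 | 42 | 29-63 | 63 - 42 = 21 | 14-28 | 70 | Week 12 |
| Week 12 | 84 | 64-98 | 98 - 84 = 14 | 7-21 | 112 | Week 16 |
| Week 16 | 112 | 99-126 | 126 - 112 = 14 | 7-21 | 140 | Week 20 |
| Week 20 | 140 | 127-161 | 161 - 140 = 21 | 14-28 | 168 | Week 26 |

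The Week 26 window is Day 162-196 and the Week 30 window is Day 197-218.

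**Step 1: replacement across visits.** Only an ET or unscheduled ECG taken before the window closes replaces the stopping ECG. Each of the five visits has 15 permitted days, 75 in all. The number of those days for which a later ECG shares the window is:

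- 7 days later: 15 × 5 = 75 of 75
- 14 days later: 8 + 15 + 8 + 8 + 15 = 54 of 75
- 21 days later: 1 + 8 + 1 + 1 + 8 = 19 of 75

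These count calendar days; they are not probabilities, because the documents set no deadline for the ET visit. Example with assumed readings: the Day 84 triplicate is 510, 508, 512, mean 1530 / 3 = 510, so the subject is stopped. The ET ECG on Day 91 is 455. Both days lie in Day 64-98, and 455 is tabulated for Week 12.

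**Step 2: off-drug ECGs in treatment rows.** With Visit 9 at last dose + 28, a last dose on Day 1 to 168 gives Day 29 to 196, so the ECG is labelled Week 6 to Week 26. Only a last dose after Day 168 reaches the Week 30 row (169 + 28 = 197). With Visit 9 at +21 to +35 days, the five cases in the table still all land in a treatment row. No QTcF event is needed for this step.

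**Step 3: last value against mean, within a visit.** If repeats or triplicate readings are recorded separately, the readings 512, 500, 492 have mean 1504 / 3 = 501.3, which meets the criterion, while 492 is tabulated.

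How often this could happen depends on a within-visit SD that the documents do not give. Given a triplicate mean *m* and SD *s*, the last reading is distributed as N(*m*, 2*s*²/3), so P(last ≤ 500) = Φ(-(*m* - 500) / (*s*√(2/3))). For an assumed *s* of 5 and 12 msec:

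| Mean of 3 | *s* = 5 | *s* = 12 |
|---|---|---|
| 503 | 0.231 | 0.380 |
| 505 | 0.110 | 0.305 |
| 510 | 0.007 | 0.154 |

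These figures are illustrative only.

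**Step 4: how likely a stop is.** Exclusion criterion 17 generally bars QTcF of 450 msec or more in males and 470 or more in females. Passing 500 then needs a rise of more than 500 - 450 = 50 or 500 - 470 = 30 msec. Subjects with QRS above 120 msec may enter with QTcF just under 500. The number of stops is unknown and may be zero.

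**The case against.** The strongest reply is that nothing is lost from reporting. The ECG listing is by subject, visit and time point, and listings include unscheduled visits. Disposition gives the reason for discontinuation by arm. If the event is recorded as an adverse event, it also appears in the outputs for events leading to discontinuation. In a small trial that was stopped early, one case is easy to find in a listing. Protocol 1.3 singles out liver toxicity, not QT, as the risk to watch, so threshold tables for liver tests alone are understandable. All of this stands, and it limits the weight of the point. It does not make the only ECG summary show the right value.

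Four stronger readings are tempting, and the documents do not support them:

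- **That SAP and protocol contradict each other.** A stopping decision and a descriptive table may use different values.
- **That a QTcF stop will be hidden.** If the ET visit is done at the stopping visit, no later ET ECG replaces the stopping ECG. If ET falls after the window closes, the stopping ECG stays in its row. If the central vendor delivers averaged triplicates, that part of Step 3 falls away; the SAP does not say whether it does.
- **That Visit 9 ECGs mask the stopping value.** In the five cases tabulated they land in a later row. They share the row only at the edges, for example a stop on Day 35 with Visit 9 on Day 63. Attendance at Visit 9 after an early stop is also inferred from Protocol 6.4.1 and 6.4.1.5; Protocol 7.4.2 expressly asks only for the ET visit.
- **That the Day 1 post-dose ECG is left out.** The windows open on Day 2, but SAP 10.6.3 summarizes by visit and does not exclude Day 1.

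**Conclusion.** The point holds as a gap in the safety summaries. Followed as written, SAP 9.6 and 10.6.3 allow an off-drug or last-repeat ECG to stand in for the on-drug mean that triggered a stop, and no other planned ECG summary would show it. The masking case requires a QTcF stop and a later or lower ECG in the same window or visit; its frequency cannot be derived from the documents. The mixing of off-drug ECGs into treatment rows is broader. It applies to any subject with a last dose by Day 168 who attends Visit 9 at 28 days, whatever the QTcF. No loss of precision and no missing source data are claimed. This is a cheap improvement worth making, not an error that undermines the safety analysis.

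**What to change.** Change the SAP only; leave Protocol 5.8 as it is.

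1. **SAP 10.6.3:** use the mean of the triplicate at each time point, at baseline and after, and the mean of the 3 ECGs where repeats are taken under Protocol 5.8.
2. **SAP 9.6:** define on-treatment ECGs as those from first dose through a short fixed interval after the last dose, for example through the following day. Later ECGs do not replace an on-treatment ECG and go to a separate off-treatment row. A cut at the last dose itself would not work: in-clinic ECGs are taken about 30 minutes after dosing, so it would remove each completer's Week 26 ECG and the stopping ECG itself.
3. **New table by arm:** worst on-treatment triplicate-mean QTcF, including Day 1 post-dose and unscheduled ECGs, with the count above 500 msec. It is still needed after items 1 and 2, because a later ECG within the on-treatment interval can still be the last in its window. It also supplies a frequency of the kind Protocol 8.4 foresees.

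The cost is slight extra programming and fewer ECGs in the treatment-visit rows. No new ECGs and no protocol amendment are needed. If the vendor already delivers averaged triplicates, the triplicate part of item 1 costs nothing.
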